**Table 1 Actual Dose Assignment**

Compliance of planned dose	DLT Status	Compliance relative to other pre-specified dose levels	Actual dose
> 100%	Any	≥ 80% a higher pre-specified dose level	Higher pre-specified dose level
> 100%	Any	< 80% a higher pre-specified dose level (or no higher dose level)	Planned dose level
≤ 100%	DLT	Any	Planned dose level
≥ 80% and ≤ 100%	No DLT	Any	Planned dose level
< 80%	No DLT	≥ 80% of a lower pre-specified dose level	Lower pre-specified dose level
< 80%	No DLT	< 80% of the lowest pre-specified dose level (or no lower dose level)	Lowest received pre-specified dose level*

\*Patient is not evaluable for DLT analysis set

Note: In case a subject received >120% cumulative dose of the planned dose but ≤ 80% of the next higher pre-specified dose the data of this subject will not be considered in Pd and efficacy summary outputs. The data will be displayed in listings and line plots but with a footnote stating the actual cumulative dose.

In the event there are subjects whose 'actual' dose differs from the planned dose, disposition, compliance and exposure will be described by both planned and 'actual' dose.

**Period definition for Part 1B (Food effect Cohort)**

For analyses related to food effect assessments, the following timepoints are defined and mapped to the visit days in the Schedule of Activities for the preliminary food effect assessments in the protocol:

**Table 2 Definition of Periods including preliminary food effect assessments**

Food Effect Assessment Period -Fasted		Food Effect Assessment Period -Fed*		Part 1A Schedule	
Analysis Day	Visit Day mapped from Schedule of Activities	Analysis Day	Visit Day mapped from Schedule of Activities	Analysis Day	Visit Day mapped from Schedule of Activities
Fasted Day 1	Day -7 or Day 1	Fed Day 1	Day -7 or Day 1	Period 1 Day 5	Day 5
Fasted Day 2	Day -6 or Day 2	Fed Day 2	Day -6 or Day 2	Period 1 Day 6	Day 6
Fasted Day 3	Day -5 or Day 3	Fed Day 3	Day -5 or Day 3	Period 1 Day 7	Day 7
Fasted Day 4	Day -4 or Day 4	Fed Day 4	Day -4 or Day 4	Period 1 Day 8	Day 8

\*The fed meal condition is planned to be a standard low-fat meal.

Note, that Food Effect Assessment is defined until Day 4 pre-dose. After Day 4, assessments are continued according to Part 1A Schedule of Activities (Period 1 Day 8, Period 1 Day 15, etc.). All cross-over design related analysis in Part 1B refers to the data collected within the timeframe of food effect assessment only (Day -7 until Day 4 per Schedule of Activities for Part 1B).

**Listings**

In the individual participant data listing all individual data for each study part (Part 1A and Part 1B) will be listed as measured. Repeated and unscheduled measurements will be included in the listings. All listings will be sorted by dose level, participant ID, and/or nominal time point, as appropriate. Data which are measured before administration of the administration of study intervention will be sorted by participant number and nominal time point (if appropriate).

**Tables and Descriptive Statistics**

All data will be summarized by study part (Part 1A and Part 1B), dose level (and regimen if different regimens are tested), dietary status ("Fed" and "Fasted"), day, and/or nominal time point, as appropriate. Different dose levels will generally be presented in increasing order. A total column is also presented. Repeated and unscheduled measurements included in the listings will not be used

for statistical analyses or summaries, unless the repeated measurement was performed due to unreliable values/technical reasons, e.g., clotted samples.

### **Presentation of continuous and qualitative variables**

Unless otherwise specified, continuous variables will be summarized using descriptive statistics, i.e. the number of participants with non-missing values (n), mean, standard deviation, median, 25th percentile (Q1) and 75th percentile (Q3), minimum, and maximum, 95% CIs for the mean, as appropriate.

Mean, median, Q1, Q3, Min, and Max will have the same precision as collected in SDTM datasets for non-derived data. Standard deviation will be presented with one digit more than the mean. Percentage and percent change from baseline will be reported using one decimal digit, if not specified otherwise. Derived data such as duration and “time since” variables (see Section 9.3) will be displayed with one decimal digit, unless stated otherwise.

If there are no missing values, the number of participants with missing values should be indicated by a 0.

Qualitative variables will be summarized by frequency counts and percentages. Unless otherwise stated the calculation of proportions will be based on the number of participants in the analysis set of interest. Therefore, counts of missing observations will be included in the denominator and presented as a separate category.

In case the analysis refers only to certain visits, percentages will be based on the number of participants still present in the trial at that visit, unless otherwise specified.

Descriptive statistics by nominal visit or time point, e.g. for laboratory measurements, will include only data from scheduled visits. Unscheduled visits will be included in the derivation of baseline or worst on-treatment values.

#### Significance level:

All statistical tests mentioned in this IAP are to be regarded as exploratory. No formal statistical hypothesis will be tested. If confidence intervals are to be calculated, these will be two-sided with a confidence probability of 95%, unless otherwise specified in this IAP.

#### Software

All analyses will be performed using SAS® Software version 9.4 or higher or R ([www.r-project.org](http://www.r-project.org)), Version 3.5.1 or higher.

## **9.1 Data handling after Cut-off Date**

By its nature, data after cut-off may be incomplete and subject to further change and will not be used for summary statistics, statistical analyses, listings or imputations.

Stop dates are not affected by this rule, e.g. a stop date of Adverse Events (AEs), which starts prior to the cut-off, but stops after date of cut-off, will not be changed.

These rules will be applied to all analyses performed for the primary analysis. For the final (follow-up) analysis no cut-off date will be applied: the analysis will be performed only after all the data have been collected, fully cleaned and the database has been locked.

## 9.2 Definition of Baseline and Change from Baseline

### Definition of baseline:

#### Part 1A:

In general, the last non-missing measurement prior to the first study intervention administration will be used as the baseline measurement.

#### Part 1B:

In general (if not otherwise specified), the last non-missing measurement prior to the first study intervention administration will serve as the baseline measurement for efficacy as well as for safety analyses (irrespective of dietary status).

For food effect analyses on pre-defined endpoints, the 'baseline' refers to the last scheduled measurement before administration of study intervention in each food effect assessment period. However, if a participant is missing the baseline collection, the previous non-missing evaluation could become the baseline value (e.g. from screening/admission). If no baseline value exists, then the baseline value and the respective change from baseline will be treated as missing.

If an assessment that is planned to be performed before study intervention per protocol is performed on the same day as the start of study intervention, but the assessment time is not available, it will be assumed that it was performed prior and will be considered as baseline.

If a scheduled pre-dose measurement actually occurred post-dose, then the corresponding measurement will be analyzed similar to an unscheduled post-dose measurement.

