1.3 Schedule of Activities

The Schedule of Activities for Part 1A (M4076 Monotherapy Dose Escalation) daily dosing schedule of this study is provided in [Table 1](#). Additional assessments may be performed at unscheduled time points if clinically indicated at the Investigator's discretion. To facilitate timely administration of study intervention, safety laboratory samples may be obtained up to 3 days before dosing. If laboratory samples are drawn before the day of dosing, they should be recorded in the case report forms (CRF) corresponding to the day of planned M4076 administration. The Part 1A pharmacokinetic (PK), electrocardiogram (ECG) and pharmacodynamic (Pd) biomarker assessments schedule is detailed in [Table 3](#).

The Schedule of Activities for Part 1B (preliminary Food Effect Assessment) is provided in [Table 2](#). The Part 1B PK, ECG, and Pd biomarker assessments schedule is detailed in [Table 4](#).

For Part 1A, potential variations in study intervention schedules and schedule of activities due to alternative dosing schedules are found [Appendix 7](#). Please see Sections [4.1.1](#) and [4.1.2](#), and [Appendix 12](#) for details on model for Bayesian dose escalation.

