Vital Signs	X	X					X				Vital signs are to be measured as follows: 
Day -7 and Day 1, at predose (within approximately 30 to 60 minutes prior) and

Assessment and Procedures	Screen	Food Effect Assessment									Treatment	Notes
Day	D-28 to -8	-7	-6	-5	-4	-3 to -1	1	2	3	4		
Visit Window (days)							-1					Day 1 assessments that could be completed on Day -1 are limited to physical examination, height/weight, and ECOG performance status.
												• 4 hours (\pm 1 hour) postdose
Serum Chemistry	X	X					X					See Appendix 6 for details.
Hematology and Coagulation (PT, aPTT, INR)	X	X					X					See Appendix 6 for details.
Urinalysis	X	X					X					See Appendix 6 for details.
Standard 12-lead ECG	X											
TriPLICATE digital ECG		X					X					ECG should only be collected for participants dosed in the fasted state. See Table 4 for triPLICATE ECG details.
AE and SAE assessment	Continuous											
Concomitant medications and procedures review												

Assessment and Procedures	Screen	Food Effect Assessment								Treatment	Notes
Day	D-28 to -8	-7	-6	-5	-4	-3 to -1	1	2	3	4	
Visit Window (days)							-1				Day 1 assessments that could be completed on Day -1 are limited to physical examination, height/weight, and ECOG performance status.
Study Intervention and Treatment											
Low-fat Meal or Overnight Fasting (Fasting window: 10 hours predose to 4 hours postdose)		X	X				X				Participants in Part 1B will be randomly assigned on a 1:1 basis to 1 of 2 study intervention sequences: (1) fasted followed by fed, or (2) fed followed by fasted. After completion of food effect assessments, participants may continue to receive study intervention at RDE from D4 onward (on an empty stomach) and follow assessments as per Table 1 from D8 onwards.
M4076 Administration (single dose)		X					X			X	After D4, M4076 dosing should continue at the RDE and thereafter follow assessments as per Table 1 .
Pharmacokinetic Assessments:											
Blood – PK blood samples M4076		X	X	X	X		X	X	X	X	See Table 4 for PK sample details.
Urine PK Collection		X	X	X	X		X	X	X	X	See Table 4 for urine PK sample details.
CCI											

Assessment and Procedures	Screen	Food Effect Assessment								Treatment	Notes
Day	D-28 to -8	-7	-6	-5	-4	-3 to -1	1	2	3	4	
Visit Window (days)							-1				Day 1 assessments that could be completed on Day -1 are limited to physical examination, height/weight, and ECOG performance status.
CCI											

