### Definition of change from baseline

absolute change from baseline = visit value – baseline value

percent change from baseline =  $100 * (visit value - baseline value) / baseline value$

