## 15.5 Vital Signs

Vital sign summaries will include all vital sign assessments from the on-treatment period. All vital sign assessments will be listed, and those collected outside the on-treatment period will be flagged in the listing.

All vital sign parameters will be summarized using descriptive statistics (mean, SD, median, Q1, Q3, minimum, and maximum) presenting baseline value, maximum on treatment, and minimum on treatment as well as their changes to baseline.

The maximum changes of vital sign measurements screening/baseline to maximum changes after start of 1st study intervention will be grouped as follows:

Body temperature increase	< 1°C , 1-<2°C , 2-<3°C, ≥ 3 °C
Heart rate increase from baseline <100 bpm ; ≥ 100 bpm	≤20 bpm, >20 – 40 bpm, >40 bpm
Heart rate decrease from baseline <100 bpm ; ≥ 100 bpm	≤20 bpm, >20 – 40 bpm, >40 bpm
SBP increase from baseline <140 mmHg; ≥ 140 mmHg	≤20 mmHg, >20 – 40 mmHg, >40 mmHg
SBP decrease from baseline <140 mmHg; ≥ 140 mmHg,	≤20 mmHg, >20 – 40 mmHg, >40 mmHg
DBP increase from baseline <90 mmHg; ≥ 90 mmHg	≤20 mmHg, >20 – 40 mmHg, >40 mmHg
DBP decrease from baseline <90 mmHg; ≥ 90 mmHg,	≤20 mmHg, >20 – 40 mmHg, >40 mmHg
Respiration rate increase from baseline <20 bpm ; ≥ 20 bpm	≤5 bpm, >5 – 10 bpm, >10 bpm
Respiration rate decrease from baseline <20 bpm ; ≥ 20 bpm	≤5 bpm, >5 – 10 bpm, >10 bpm

For each participant the worst on-treatment value will be calculated. For the definition of baseline values see Section 9.2. Missing values will define a separate category.

The following summaries will be prepared for vital sign parameters as grouped above:

- Maximal shifts (changes in categories)
- Listing of highest change per participant

An additional participant data listing will present all changes from baseline reported in the highest categories.

For the cross-over design in Part 1B, vital signs will be summarized for absolute values and changes from baseline by time-point and dietary status using descriptive statistics.

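### SAP 9.2 lets a missing Part 1B period baseline be filled by an on-drug reading; for vital signs in period 2, that is what the rule literally selects

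*SAP*

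**What the plan says.** SAP 9.2 sets two baselines for Part 1B.

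- **General baseline.** The last non-missing value before the first dose "will serve as the baseline measurement for efficacy as well as for safety analyses (irrespective of dietary status"). By construction it cannot be an on-drug value.
- **Period baseline.** For food-effect analyses on endpoints described as pre-defined, "the 'baseline' refers to the last scheduled measurement before administration of study intervention in each food effect assessment period". If that value is missing, "the previous non-missing evaluation could become the baseline value (e.g. from screening/admission").

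Change is then defined as "absolute change from baseline = visit value – baseline value".

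Protocol Table 2 (Section 1.3.2) marks vital signs at screening, Day -7 and Day 1 only. Its note sets the times as "Day -7 and Day 1, at predose (within approximately 30 to 60 minutes prior) and" again at 4 hours (± 1 hour) after the dose.

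For the cross-over part, SAP 15.5 plans that "vital signs will be summarized for absolute values and changes from baseline by time-point and dietary status using descriptive statistics".

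**The concern.** The general baseline is tied to the time before the first dose. The fallback for the period baseline carries no such condition. In a two-period cross-over, the value immediately preceding a missing period 2 baseline may have been recorded after the period 1 dose. Using it subtracts one on-drug reading from another, and the result is no longer a change due to the period 2 dose.

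Vital signs matter here because the protocol lists increased heart rate as a potential risk of M4076 (Section 2.3.1, Table 5). The affected participant is distorted in one dietary column only. The error can therefore create an apparent fed-fasted difference as well as alter the size of the change.

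**Working it through.** The plan gives no figure to reproduce on this point. The check traces the fallback through the schedule, then does the arithmetic.

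**Step 1: what counts as previous when the Day 1 pre-dose value is missing**

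| Measure | Schedule before the Day 1 dose | Literal fallback | On drug? |
|---|---|---|---|
| Vital signs | Screening; Day -7 pre-dose and 4 h post-dose | Day -7, 4 h post-dose | Yes |
| Triplicate ECG | Fasted period only | Screening ECG, for a participant fasted in period 2 | No |
| Haematology, chemistry | Screening; Day -7, no post-dose time given | Day -7 sample | Not shown |
| AUC, Cmax | Not applicable | No baseline used | Not applicable |

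On ECG, Table 2 says "ECG should only be collected for participants dosed in the fasted state". A participant fasted in period 2 was fed in period 1 and so has no scheduled period 1 triplicate to borrow. On laboratory tests, Protocol 1.3 says "safety laboratory samples may be obtained up to 3 days before dosing", and no post-dose sample is scheduled in the cross-over window. The food-effect model in SAP 16.1.3 has sequence, period and treatment as fixed effects and subject within sequence as random, with no baseline term.

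**Step 2: effect on one participant**

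Let B be the undosed value, assumed the same in both periods, and let E1 and E2 be the 4-hour drug effects in periods 1 and 2.

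- Intended change in period 2: (B + E2) - B = E2.
- Change under the literal fallback: (B + E2) - (B + E1) = E2 - E1.

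The documents give no effect size, so these values are assumed, in bpm:

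- E1 = 10, E2 = 10: 0 instead of 10.
- E1 = 10, E2 = 15: 5 instead of 15.
- E1 = 10, E2 = 5: -5 instead of 5.

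**Step 3: effect on a dietary column**

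Part 1B plans 12 participants randomised 1:1, so each dietary column holds 12 profiles, 6 from each period. With equal effects E and k affected profiles in the column:

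mean = [(12 - k) × E + k × 0] / 12

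For k = 1 this is 11E/12 = 0.917E, a shrinkage of 1/12 or 8.3%.

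| Assumed E (bpm) | k = 1 | k = 2 | k = 6 (all period 2 profiles) |
|---|---|---|---|
| 5 | 4.58 | 4.17 | 2.50 |
| 10 | 9.17 | 8.33 | 5.00 |
| 20 | 18.33 | 16.67 | 10.00 |

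For k = 1 the bias is -0.42, -0.83 and -1.67 bpm respectively. If only one column is affected and the true effect is 10 bpm in both, the table shows 9.17 against 10, a spurious fed-fasted difference of 0.83 bpm.

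**The case against.** The strongest reply is that the fallback may not reach vital signs at all. It belongs to the period baseline, which SAP 9.2 reserves for food-effect analyses on pre-defined endpoints. The endpoints visibly listed under the food-effect objective are the AUC and Cmax ratios, which need no baseline. Vital signs sit among the safety analyses, where the general baseline would protect them. This stands as a real uncertainty. SAP 15.5 refers to Section 9.2 without choosing between the two baselines, and the pre-defined endpoints are not listed. Against it, the table is described as part of the cross-over analysis and is split by dietary status, and the note under SAP Table 2 confines cross-over analyses to the Day -7 to Day 4 window. That makes the period baseline the natural choice, though not a stated one.

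The second reply is that the wording is permissive (the earlier value *could* be used) and that its example is screening or admission. This also stands. A reader might infer that the SAP prescribes the on-drug reading. It only permits it and leaves the choice to whoever programs the table.

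Third, the case needs a missing period 2 baseline. SAP 9.2 narrows this by treating an untimed same-day assessment planned before dosing as pre-dose. It also opens a second route: a planned pre-dose reading actually taken after dosing is handled as an unscheduled post-dose value, which can leave the period without a baseline. No missing-data rate is given, so the frequency cannot be estimated.

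Finally, absolute values by time-point and dietary status appear in the same summary, and all vital-sign assessments are listed. An on-drug rise in heart rate would stay visible.

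**Conclusion.** The point holds as a gap in wording with a small and conditional consequence. On the scheduled visits, the only measure for which the fallback literally selects an on-drug value is vital signs in period 2. The affected participant's change becomes E2 - E1. With equal effects, each such participant lowers that column's mean change by 1/12.

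This rests on four assumptions: the period baseline governs the fed/fasted vital-sign table, the Day 1 pre-dose reading is missing, the analyst takes the rule literally despite the screening example, and the undosed value is stable between periods. If the general baseline governs instead, the effect is nil.

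Three stronger readings are tempting, and the documents do not support them.

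- **That Part 1B changes from baseline are affected generally.** The schedule does not show this for ECG or laboratory values, and the AUC/Cmax model is untouched. The pharmacodynamic sections are redacted and cannot be checked.
- **That the bias is always toward no effect.** E2 - E1 is zero only when the two effects are equal, and it turns negative when the period 1 effect is the larger.
- **That a primary endpoint is compromised.** That endpoint is the occurrence of clinically significant vital-sign changes, under the dose-toxicity objective. The categorical shift tables in SAP 15.5 appear to be anchored to the first dose. What is exposed is a supplementary descriptive table.

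**What to change.** Make two short edits.

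1. In SAP 9.2 (Part 1B), restrict the fallback to *the previous non-missing pre-dose evaluation (Day -7 pre-dose, or screening)*.
2. State, in SAP 9.2 or 15.5, that the Part 1B vital-sign tables by dietary status use the period baseline. Without this, the first edit leaves open whether the rule applies to them.

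Both use data already scheduled for collection and change no procedure. The cost is a phrase and a sentence, and the choice no longer rests with the programmer.

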### Definition of change from baseline

absolute change from baseline = visit value – baseline value

percent change from baseline =  $100 * (visit value - baseline value) / baseline value$

## 9.3 Study Day / Study Intervention Day

### Part 1A:

Day 1 is the day of start of study intervention, the day before is Day -1 (no Day 0 is defined). Study day / Study intervention day is defined relative to Day 1.

### Part 1B:

Day 1 is the day of start of study intervention, the day before is Day -1 (no Day 0 is defined). Study day / Study intervention day is defined relative to Day 1 (irrespective of dietary status), if not otherwise specified.

### **Definition of Duration and 'Time Since' Variables**

Durations in days will be calculated by the difference of start and stop date + 1 (e.g. survival time (days) = date of death – date of first study intervention + 1) if not otherwise specified.

The time since an event (e.g. time since first diagnosis) will be calculated as reference date minus date of event.

## 9.4 Conversion Factors

The following conversion factors will be used to convert days into months or years:

1 week = 7 days, 1 month = 30.4375 days, 1 year = 365.25 days.

## 9.5 Date of Last Contact

The date of last contact will be derived for participants not known to have died at the analysis cut-off using the latest complete date prior to or at the data cut-off date among the following:

Participants off study intervention:

Last known to be alive date collected on the 'Survival Follow-up' eCRF Participants on study intervention:

- AE start and end dates
- Date of last study intervention
- Date of last tumor assessment
- All participant assessment dates (blood draws [laboratory and PK], vital signs, performance status, ECG)
- Date of discontinuation on disposition eCRF pages (unless reason for discontinuation is lost to follow-up).

- Start and End date of Concomitant Medication and Procedures eCRF pages

Only dates associated with actual examinations of the participant reported in the eCRF will be used in the derivation. Dates associated with a technical operation unrelated to participant status such as the date a blood sample was processed will not be used. Assessment dates after the cut-off date will not be applied to derive the last contact date.

